6.3 Modification in Dose or Schedule

Once patients achieve morphologic complete remission with incomplete blood count recovery (CRi) (morphologic leukemia-free state, defined as less than 5% blasts in aspirate with marrow spicules and a count of ≥ 200 nucleated cells and no blasts with Auer rods, any persistence of extramedullary disease, or persistent pre-treatment morphologic abnormalities, such as pseudo-Pelger-Huet cells, ringed sideroblasts, or dysplastic megakaryocytes), administration may be decreased to 5 consecutive days to limit myelosuppressive toxicity, per treating physician. After two cycles with bone marrow blast counts $< 5\%$ and no evidence of disease by cytogenetics or immunophenotype, patients may further decrease therapy to 3 consecutive days per cycle, per treating physician.

[Redacted]

[Redacted]

[Redacted]

[Redacted]

[Redacted]

[Redacted]

[Redacted]

[Redacted]

[Redacted]

[Redacted]

[Redacted]

Genomic Predictors of Decitabine Response in AML/MDS

8.0 CORRELATIVE STUDIES SAMPLE COLLECTIONS

Bone marrow samples will be collected at Baseline, on Cycle 1 Day 10 ± 1 , and on Day 28 ± 4 of Cycle 1 and of even number cycles for correlative studies. Bone marrow aspirate (6-10 ml) will be collected and divided between two EDTA (lavender top) tubes. The bone marrow samples and peripheral blood samples should be delivered by hand to [name]. PhD, director of the Tissue Procurement Core Facility at the Siteman Cancer Center. At the Tissue Procurement Core Facility, patient identification will be removed from the samples, and the cells will be stored as frozen pellets in DMSO at 10^7 per tube. Subsequently, the samples will be thawed, and cells will be assayed.

Peripheral blood sample (3 mL) will be collected on Cycle 1 Day 4 ± 1 . Sample must be obtained 45 minutes \pm 15 minutes after beginning the infusion, before the decitabine infusion is complete, and should be obtained from the opposite arm as the infusion. The sample should be collected in a 3 mL K3EDTA tube pre-loaded with 8 mL of tetrahydrouridine (THU 500 mcg/mL), an inhibitor of cytidine deaminase. The sample should be processed by the Tissue Procurement Core Facility at the Siteman Cancer Center. Serum should be separated and stored per protocols.

9.0 EFFICACY, SAFETY AND CORRELATIVE STUDY MEASURES

A secondary endpoint of this study is to estimate morphologic complete remission rate.

9.1 Response Criteria

Patients will be assessed for response according to the IWG criteria:¹

Morphologic complete remission (CR) – Defined as morphologic leukemia-free state, defined as less than 5% blasts in aspirate with marrow spicules and a count of ≥ 200 nucleated cells and no blasts with Auer rods or any persistence of extramedullary disease. When erythroid precursors constitute less than 50% of bone marrow nucleated cells, the percentage of blasts is based on all nucleated cells; when there are 50% or more erythroid cells, the percentage blasts should be based on the nonerythroid cells. The presence of mild megaloblastoid changes may be permitted if they are thought to be consistent with treatment effect. However, persistence of pretreatment abnormalities (eg, pseudo-Pelger-Hüet cells, ringed sideroblasts, dysplastic megakaryocytes) are not consistent with CR. In addition, ANC $> 1000/\mu\text{l}$ and platelet count of $\geq 100,000/\mu\text{l}$. Patient must be independent of transfusions. No duration requirement for this designation.

Cytogenetic complete remission (CCR) – Defined as morphologic complete remission plus a reversion to a normal karyotype. For this study, reversion of a normal karyotype is defined as no clonal abnormalities detected in a minimum of 20 mitotic cells.

Morphologic complete remission with incomplete blood count recovery (CRi) – Defined as morphologic complete recovery with the exception of neutropenia $< 1000/\mu\text{l}$ or thrombocytopenia $< 100,000/\mu\text{l}$.

Partial remission (PR) – Requires that the above criteria for complete remission be met, with the following exceptions: decrease of $\geq 50\%$ in the percentage of blast to 5-25% in the bone marrow aspirate. A value of $\leq 5\%$ blasts in bone marrow with Auer rods present may also be considered a partial remission.

Treatment failure – Includes all patients who did not achieve a complete or partial remission following 4 cycles of therapy.

Recurrence/morphologic relapse - Relapse following complete remission is defined as reappearance of blasts in the blood or the finding of $\geq 5\%$ blasts in the bone marrow, not attributable to any other cause. New dysplastic changes are considered a relapse. If there are no blasts in the peripheral blood and 5-20% blasts in the bone marrow, bone marrow biopsy should be repeated in > 1 week to confirm relapse.

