9.1 Response Criteria - AML

AML Patients will be assessed for response according to the IWG criteria:¹

Morphologic complete remission (CR) – Defined as morphologic leukemia-free state, defined as less than 5% blasts in aspirate with marrow spicules and a count of ≥ 200 nucleated cells and no blasts with Auer rods or any persistence of extramedullary disease. When erythroid precursors constitute less than 50% of bone marrow nucleated cells, the percentage of blasts is based on all nucleated cells; when there are 50% or more erythroid cells, the percentage blasts should be based on the nonerythroid cells. The presence of mild megaloblastoid changes may be permitted if they are thought to be consistent with treatment effect. However, persistence of pretreatment abnormalities (eg, pseudo-Pelger-Hüet cells, ringed sideroblasts, dysplastic megakaryocytes) are not consistent with CR. In addition, ANC $> 1000/\mu\text{l}$ and platelet count of $\geq 100,000/\mu\text{l}$. Patient must be independent of transfusions. No duration requirement for this designation.

Cytogenetic complete remission (CCR) – Defined as morphologic complete remission plus a reversion to a normal karyotype. For this study, reversion of a normal karyotype is defined as no clonal abnormalities detected in a minimum of 20 mitotic cells.

Morphologic complete remission with incomplete blood count recovery (CRi) – Defined as morphologic complete recovery with the exception of neutropenia $< 1000/\mu\text{l}$ or thrombocytopenia $< 100,000/\mu\text{l}$.

Partial remission (PR) – Defined as meeting the above criteria for complete remission, with the following exceptions: decrease of $\geq 50\%$ in the percentage of blast to 5-25% in the bone marrow aspirate. A value of $\leq 5\%$ blasts in bone marrow with Auer rods present may also be considered a partial remission.

Stable Disease (SD) – Defined as not meeting the definitions of CR, CRi, PR, PD, or recurrence/morphologic relapse.

Progressive disease (PD) – Defined as a clear increase in bone marrow blast count, typically a greater than 50% increase compared with baseline, or new extramedullary disease. Patients with a $> 50\%$ increase in peripheral blast count with an increase of the total peripheral white blood cell count to $> 10,000/\mu\text{l}$ should undergo evaluation by bone marrow biopsy to access for progressive disease.

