9.2 Response Criteria - MDS

MDS Patients will be assessed for response according to the IWG criteria:⁶⁹

Complete remission (CR) – Defined as $\leq 5\%$ myeloblasts with normal maturation of all cell lines in the bone marrow and peripheral blood values of Hgb ≥ 11 g/dL, Platelets $\geq 100 \times 10^9/L$, Neutrophils $\geq 1.0 \times 10^9/L$, and 0% blasts. Persistent dysplasia does not exclude CR but will be noted.

Marrow Complete Response (Marrow CR) – Defined as $\leq 5\%$ myeloblasts in the bone marrow and a decrease by $\geq 50\%$ from pretreatment values, but not meeting the definition of CR above.

Partial Remission (PR) – Defined as meeting the definition of CR above with a decrease of myeloblasts in the bone marrow by $\geq 50\%$ from pretreatment values, but absolute myeloblasts still $>5\%$.

Stable Disease (SD) – Defined as not meeting the definitions of CR, Marrow CR, PR, SD, PD, or recurrence/morphologic relapse.

Progressive Disease//Relapse (PD) – Defined as $\geq 50\%$ increase in blasts to $> 5\%$ blasts (for patients with less than 5% blasts at baseline only), $\geq 50\%$ increase to $> 10\%$ blasts (for patients with 5-10% blasts at baseline only), $\geq 50\%$ increase to $> 20\%$ blasts (for patients with 10-20% blasts at baseline only), $\geq 50\%$ increase to $> 30\%$ blasts (for patients with 20-30% blasts at baseline only) or any of the following: At least 50% decrement from maximum remission/response in granulocytes or platelets, reduction in Hgb by ≥ 2 g/dL, or New or worsened transfusion dependence not related to study drug toxicity. Or for patients with a CR, Marrow CR, or PR as defined above and subsequently development of one of the following: Return to pretreatment bone marrow blast percentage, decrement of $\geq 50\%$ from maximum remission/response levels in granulocytes or platelets, or reduction in Hgb concentration by ≥ 1.5 g/dL or transfusion dependence.

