14.2.3 Secondary Endpoint Analyses

The overall response rate (CR/CRi/PR) and complete response rate (CR/CRi) will be compared with historical controls[2], and the 95% confidence intervals will be provided.

The rate of patient specific mutation clearance after 10, 28, and 56 days of therapy will be determined using an Illumina based platform. We will compare the rate of mutation clearance between the patients who achieve a CR/CRi after 4 cycles and those who do not. We anticipate that we will identify between 6 and 25 exonic SNVs per case (the range obtained with >200 AML samples sequenced to date with whole genome or exome sequencing), and that the expected 95% confidence

interval of the mean variant allele frequency will be $\pm 2.56\%$ and $\pm 1.25\%$, respectively, if we assume an anticipated standard deviation of 3.2% within the same clone. The change of tumor burden over time and its association with clinical response will be assessed using 2-way ANOVA for repeated measurement data, followed by the ad-hoc multiple comparisons for between-group differences (e.g., responders vs. non-responders) at given time points as well as the between-time differences within each group. The resultant critical P values will also be corrected using permutation analysis for multiple testing.

The steady-state plasma decitabine concentration on day 4 ± 1 will be measured and correlated with clinical overall response.

The percent decrease in bone marrow methylcytosine will be calculated on day 10 ± 1 . We will compare this reduction with previously published data and between the patients who achieve CR/CRi and those who do not. The correlation of peak plasma levels of decitabine with response will be assessed using 2-sample t-test or Mann-Whitney non-parametric rank-sum test as appropriate. The change of total bone marrow DNA methylcytosine from baseline and its association with both steady-state plasma drug levels and response will be assessed using 2-way ANOVA for repeated measurement data, followed by the ad-hoc multiple comparisons for between-group differences (e.g., responders vs. non-responders) and between-time differences. Similar analyses will be performed for the correlation of expression profiles and SNP analysis with pharmacokinetic data.

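### AML response criteria leave an ANC of exactly 1000/µl in neither CR nor CRi, so a marrow remission at that count falls to stable disease

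*Combined protocol and SAP*

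**What the plan says.** The file holds several versions of the protocol. The latest shown is the one with its statistics in Section 14, and its Section 9.1 (AML criteria) sets these count limits:

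- **CR:** a leukemia-free marrow and transfusion independence. For neutrophils, "In addition, ANC $> 1000" per µl; for platelets, "platelet count of $\geq 100,000" per µl. No minimum duration is required.
- **CRi:** "Defined as morphologic complete recovery with the exception of neutropenia $< 1000" per µl, or platelets below 100,000/µl.
- **PR:** the CR criteria, except that marrow blasts have fallen by at least half to 5-25%, or are at most 5% with Auer rods. Earlier versions say the same: "Requires that the above criteria for complete remission be met, with the following exceptions".
- **Stable disease:** "Defined as not meeting the definitions of CR, CRi, PR, PD, or recurrence/morphologic relapse".

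Section 9.2 (MDS criteria) sets the CR neutrophil limit as "Neutrophils $\geq 1.0" x 10^9/L. Marrow CR in MDS has no neutrophil limit.

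Section 14.2.3 shows which categories count as response: "The overall response rate (CR/CRi/PR) and complete response rate (CR/CRi) will be compared with historical controls[2"]. Section 14.2.2 takes overall response as the outcome of the primary mutation analysis and assumes 45% CR/CRi for power.

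The AML neutrophil limits are the same in every version in the file. The earliest versions have one set of criteria for all patients and no stable disease category. There, a patient outside the remission categories falls under treatment failure: "Includes all patients who did not achieve a complete or partial remission following 4 cycles of therapy".

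**The concern.** CR and CRi are meant to divide the patients whose marrow has cleared, according to whether their counts have recovered. For platelets they do: one limit is at least 100,000 and the other is below it. For neutrophils both limits are strict, so one value belongs to neither.

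The result is out of order. With the same marrow and platelets, a patient with a slightly lower count is a responder, a patient at 1000 is not, and a patient with a slightly higher count is again a responder. That cannot be intended.

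Response is the dependent variable of the primary analysis. It also enters treatment failure and event-free survival (Section 9.4.1). Section 14.3 plans 25 patients at one center and 100 more from at least two others. Without a rule for a count of 1000, assessors must choose a category themselves and may choose differently.

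**Working it through.** No stated figure depends on this boundary, so there is none to reproduce. The check applies the rules as written and then sizes the effect.

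**Step 1. Classify by count.** Assume a leukemia-free marrow and transfusion independence. CRi can be read strictly (every CR count criterion is met unless a listed exception covers it) or leniently (either exception is enough).

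| ANC (/µl) | Platelets ≥ 100,000/µl | Platelets < 100,000/µl |
|---|---|---|
| 500 or 999 | CRi | CRi |
| 1000 | neither, on both readings | neither if strict; CRi if lenient |
| 1001 | CR | CRi |

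The gap is certain only with platelets of at least 100,000/µl.

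**Step 2. Look for a fallback.** PR does not catch the patient. It carries over the CR neutrophil limit and needs either 5-25% blasts or Auer rods. Progression and relapse do not apply. What remains is stable disease, which is outside both CR/CRi and CR/CRi/PR.

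**Step 3. Effect per patient.** With 100 evaluable patients and 45 responders expected, one affected patient gives 44/100 = 44% and two give 43/100 = 43%, so 1 point each.

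**Step 4. How many patients.** The documents do not say how ANC is rounded. If exact counts are used, the number is near zero. For an upper end, assume reporting to one decimal (x 10^9/L) and an even spread over 0.5-3.0. About one value in (3.0 − 0.5)/0.1 = 25 is then 1.0, or 4%, and 0.04 × 45 = 1.8 patients at a single marrow. This ignores the platelet condition and other assessments, both of which lower it. A fair assumed range is 0 to 2.

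**Step 5. Effect on power.** Take the Table 3 row with 20% mutation frequency and a difference of 0.35. The non-carrier rate is 0.45 − 0.20 × 0.35 = 0.38 and the carrier rate is 0.73, with 20 carriers and 80 non-carriers. Use

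power = Φ[(d − 1.96 × SE0)/SE1],

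where SE0 uses the pooled rate and SE1 the separate rates.

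- None lost: SE0 = √(0.45 × 0.55 × (1/20 + 1/80)) = 0.1244; SE1 = √(0.73 × 0.27/20 + 0.38 × 0.62/80) = 0.1131; power = Φ(0.94) = 82.6%.
- Two of 45 responders lost, in proportion in both groups: the rates become 0.73 × 43/45 = 0.698 and 0.38 × 43/45 = 0.363, so d = 0.334; SE0 = 0.1238; SE1 = 0.1159; power = Φ(0.79) = 78.6%. With one lost it is 80.6%.

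Even at the upper end, power stays close to the planned 80%.

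**The case against.** The strongest objection is that the patient need not stay a non-responder. CR has no duration requirement. Blood counts are weekly in Cycle 1, at least every other week after that, and also taken on Day 1 of each cycle. Response marrows fall at the end of Cycles 1, 2, 4 and 6, and treatment failure is judged only after four cycles. A count of 999 or 1001 at another qualifying assessment gives CRi or CR. This stands, and it is why the point is limited to the category at a given assessment.

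A reader might infer more than the documents support in three ways:

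- **That one or two responders will be lost.** The 1.8 rests on assumed rounding and an assumed spread. Section 9.1 states its limits per µl, and nothing says ANC is recorded to one decimal.
- **That a mutation comparison is distorted.** One lost carrier in 20 would move the carrier rate by 5 points, but that is not the expected effect. At the assumed 4%, the expected number of lost carriers is 20 × 0.45 × 0.04 = 0.36 with no association, or 20 × 0.73 × 0.04 = 0.58 at the Table 3 difference, before any rescue. Nothing suggests that the gap favors carriers or non-carriers.
- **That it biases AML against MDS in the pooled analysis.** Only versions with separate MDS criteria show the contrast. There, MDS CR also requires hemoglobin of at least 11 g/dL, so the two rules already differ by more than this limit.

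Two textual points also count. Section 6.3 of the earliest versions describes CRi as a leukemia-free marrow without giving a neutrophil limit, which would give an assessor grounds for CRi at 1000. The latest version instead refers back to Section 9.0. Section 9.1 also cites published working-group criteria, and whether the strict limits come from there cannot be checked here. Neither point closes the gap in the current text.

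**Conclusion.** The point holds as a defect in the wording of the response definition, with minor consequences. In the latest version, a leukemia-free marrow with platelets of at least 100,000/µl and an ANC of exactly 1000/µl is stable disease at that assessment, while a neighboring count on either side is a response. This follows from the text and needs no assumption.

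Its size does need one: about 0 to 2 patients, each worth 1 point of the response rate, and only where no other assessment qualifies. The documents do not support calling it a threat to the primary analysis or its power. It is worth correcting because the primary outcome should give every evaluable patient one sensible category.

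**What to change.** In Section 9.1, reconcile the CR and CRi neutrophil limits so that they meet at 1000/µl with no value left uncovered, as the platelet limits already do. Also state whether a count of 1000 with platelets below 100,000/µl is CRi, and how reported ANC values are rounded before the limit is applied.

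The CR/CRi and CR/CRi/PR rates are the same whichever category takes 1000. The sponsor should choose the side and check it against Section 6.3, where CR with complete cytogenetic response and CRi each open different schedule options. The Section 9.2 limit for MDS is a reference for consistency, not a reason to prefer a side.

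The cost is one symbol plus a sentence or two, with no new data and no change to the sample size. Assessments already scored at exactly 1000/µl, if any, should be re-read under the amended rule.

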9.2 Guidelines for Evaluation of Disease

Bone marrow biopsy should be performed at baseline for both the correlative study and clinical evaluation. Bone marrow biopsy should be performed on Day 28 \pm 4 of cycle 1 and on Day 28 \pm 4 of each even cycle for clinical disease assessment.

Peripheral blood counts will be followed by weekly CBC with differential and platelets. After the first cycle, this may be changed to every other week or monthly at the discretion of the treating physician.

9.3 Progressive Disease

Progressive disease is defined as a clear increase in bone marrow blast count, typically a greater than 50% increase compared with baseline. Patients with progressive disease will be removed from the study.

Patients may also be removed from the study for progressive disease based on evidence of new extramedullary disease or based on the clinical judgment of the treating physician.

Patients with a $>$ 50% increase in peripheral blast count with an increase of the total peripheral white blood cell count to $>$ 10,000/ μ l should undergo evaluation by bone marrow biopsy regardless of the cycle number.

9.4 Other Secondary Efficacy Measures

9.4.1 Overall Survival and Event-free Survival

Overall survival is defined as the date of first dose of study drug to the date of death from any cause. Patients still alive at the time of the final analysis will be right-censored.

Event-free survival is defined as the interval from the date of first dose of study drug to date of treatment failure, recurrence, death due to any cause, or loss to follow up.

9.4.2 Duration of Remission and Relapse-free Survival for Patients Having Complete Remission

Duration of complete remission is defined as the interval from the date that complete remission is documented to the date of recurrence, death due to any cause, or loss to follow-up.

Relapse-free survival is defined only for those patients achieving a complete remission. It is defined as the interval from the date of first documentation of a

leukemia-free state to the date of recurrence, death due to any cause, or loss to follow up.

9.4.3 Safety

Safety evaluation will include assessments of adverse experiences, medical history, physical examinations, vital signs, and laboratory assessments at baseline and throughout the study period. Local laboratories may be used for this study.

10.0 ADVERSE EVENT REPORTING

10.1 Adverse Events (AEs)

Definition: any unfavorable medical occurrence in a human subject including any abnormal sign, symptom, or disease.

Grading: the descriptions and grading scales found in the revised NCI Common Terminology Criteria for Adverse Events (CTCAE) version 4.0 will be utilized for all toxicity reporting. A copy of the CTCAE version 4.0 can be downloaded from the CTEP web site: <http://ctep.cancer.gov/reporting/ctc.html>.

Attribution (relatedness), Expectedness, and Seriousness: the definitions for the terms listed that should be used are those provided by the Department of Health and Human Services' Office for Human Research Protections (OHRP). A copy of this guidance can be found on OHRP's website: (<http://www.hhs.gov/ohrp/policy/AdvEvtntGuid.htm>).

10.2 Unanticipated Problems

Definition:

- unexpected (in terms of nature, severity, or frequency) given (a) the research procedures that are described in the protocol-related documents, such as the IRB-approved research protocol and informed consent document; and (b) the characteristics of the subject population being studied;
- related or possibly related to participation in the research (in this guidance document, possibly related means there is a reasonable possibility that the incident, experience, or outcome may have been caused by the procedures involved in the research); and
- suggests that the research places subjects or others at a greater risk of harm (including physical, psychological, economic, or social harm) than was previously known or recognized.

